#### **5.5.1.2. Intensive Chemotherapy**

Refer to the local package inserts (or SPC) or Investigational Product Manual for detailed formulation, preparation and dispensing information for cytarabine and daunorubicin. An overview of the treatment algorithm is shown in [Figure 2](#) and specific doses and dosing frequencies are provided in [Table 7](#).

**Figure 2. Intensive Chemotherapy Treatment Algorithm: Glasdegib or Placebo in combination with Cytarabine and Daunorubicin**

**Figure footnotes:**

a. If <5% bone marrow blasts, the investigator may either treat with a second Induction therapy or proceed to Consolidation therapy with single-agent cytarabine and/or post remission HSCT.

- b. Consolidation with cytarabine 3 g/m^2 IV for adults <60 years and 1 g/m^2 for adults ≥60 years over 3 hours twice daily (BID) on Days 1, 3, and 5, every 28 days for up to 4 cycles. Alternative single-agent cytarabine consolidation schedules may be used per local prescribing information.
- c. Resume glasdegib or placebo 30-60 days post day of stem cell infusion, once there is confirmed ANC engraftment ( $\geq 0.5 \times 10^9/L$ ) for 3 consecutive days with no growth factor support, no ≥Grade 2 ongoing GVHD, and no ongoing SAEs that prevent resuming glasdegib or placebo in the judgment of the investigator. Following Post Consolidation or Post Remission HSCT, modify treatment based on 2 matching and consecutive MRD negative results (by central laboratory) when they are available.
- d. Post consolidation bone marrow assessment should be conducted after chemotherapy-based consolidation period. For patients proceeding to HSCT, post-HSCT bone marrow assessment will be conducted approximately 3 months after HSCT. This post-HSCT bone marrow assessment may be later than the resumption of glasdegib/placebo 30-60 days post HSCT.

### **Glasdegib or Placebo**

Experimental Therapy: Glasdegib 100 mg PO QD or matching placebo will be administered by mouth daily beginning on Day 1 and is to continue up to 2 years post randomization until treatment failure, hematologic relapse, objective disease progression, patient refusal, unacceptable toxicity, unexpected pregnancy, death, or consent withdrawal.

- Subjects will receive daily glasdegib 100 mg PO or matching placebo up to 2 years after randomization or until they have CR MRD-negative disease post consolidation. Glasdegib or placebo therapy will continue throughout Induction(s) and Consolidation Therapy regardless of any delays/modifications in the chemotherapy treatment.

### **Cytarabine**

- Separate cytarabine dosing and schedules will be used for Induction and Consolidation per the local package insert (or SPC) or Investigational Product Manual (or SPC).
- **Induction 1:** Cytarabine will be administered (in parallel to daunorubicin) at a dose of 100 mg/m^2 daily by continuous IV infusion for 7 days (Days 1-7).
- **Induction 2,** if indicated based on ≥5% marrow blasts (or investigator judgment if <5% bone marrow blasts), The Investigator may choose either cytarabine 100 mg/m^2 IV daily on Days 1-5 or Days 1-7. Dose must be recalculated if the weight changes by >10%.

### **Daunorubicin Dosing (Induction Only):**

- During **Induction 1**, daunorubicin 60 mg/m^2 daily IV on Days 1-3.

- **Induction 2**, if indicated based on  $\geq 5\%$  bone marrow blasts (or investigator judgment if  $< 5\%$  bone marrow blasts), the Investigator will choose either daunorubicin  $60 \text{ mg/m}^2$  IV daily on Days 1-2 or Days 1-3 with cytarabine. If clinical signs or symptoms of cardiac dysfunction are observed, multigated acquisition scan/echocardiogram (MUGA/ECHO) must demonstrate a LVEF  $\geq 45\%$  before initiation of Induction 2. Dose must be recalculated if the weight changes by  $> 10\%$ .
- If  $< 5\%$  bone marrow blasts: treatment with either or both of the following if a second Induction is not selected (per investigator judgment):
  - Consolidation with single-agent cytarabine  $3 \text{ g/m}^2$  IV for adults  $< 60$  years and  $1 \text{ g/m}^2$  for adults  $\geq 60$  years over 3 hours twice daily (BID) on Days 1, 3, and 5, every 28 days for up to 4 cycles or alternative single-agent cytarabine consolidation schedules may be used per local prescribing information.
  - HSCT per local standard of care.

A detailed dosing schedule is found in Table 7.

Table 7. Intensive Chemotherapy Doses and Dose Frequency: Glasdegib or Placebo in Combination with Daunorubicin and Cytarabine		
Days	Induction Therapy	
	Backbone Chemotherapya	Experimental Therapya,b,c
1-3	Administer Daunorubicin $60 \text{ mg/m}^2$ IV Administer cytarabine $100 \text{ mg/m}^2$ IV	Administer glasdegib $100 \text{ mg}$ PO or placebo PO
4-7	Administer cytarabine $100 \text{ mg/m}^2$ IV	
$\geq 8^d$		
Days	Second Induction if <math>\geq 5\%</math> bone marrow blasts or investigator judgement for <math>< 5\%</math> bone marrow blasts (Option 1: '5+2')	
	Backbone Chemotherapya	Experimental Therapya,b,c
1-2	Administer Daunorubicin $60 \text{ mg/m}^2$ IV Administer cytarabine $100 \text{ mg/m}^2$ IV	Administer glasdegib $100 \text{ mg}$ PO or placebo PO
3-5	Administer cytarabine $100 \text{ mg/m}^2$ IV	
$\geq 6^d$		
Days	Second Induction if <math>\geq 5\%</math> bone marrow blasts or investigator judgement for <math>< 5\%</math> bone marrow blasts (Option 2: '7+3')	
	Backbone Chemotherapya	Experimental Therapya,b,c
1-3	Administer Daunorubicin $60 \text{ mg/m}^2$ IV Administer cytarabine $100 \text{ mg/m}^2$ IV	Administer glasdegib $100 \text{ mg}$ PO or placebo PO
4-7	Administer cytarabine $100 \text{ mg/m}^2$ IV	
$\geq 8^d$		
Days	If <math>< 5\%</math> bone marrow blasts, Consolidation (Option 1): 1-4 Cycles of Consolidation (28 day cycles)	
	Backbone Chemotherapya	Experimental Therapya,b
1	Administer cytarabine $1$ or $3 \text{ g/m}^2$ IV twice daily (BID)	Administer glasdegib $100 \text{ mg}$ PO or placebo PO
2		

Table 7. Intensive Chemotherapy Doses and Dose Frequency: Glasdegib or Placebo in Combination with Daunorubicin and Cytarabine		
3	Administer cytarabine 1 or 3 g/m  IV twice daily (BID)	
4		
5	Administer cytarabine 1 or 3 g/m  IV twice daily (BID)	
≥6 d		
Up to 2 years after randomization d		
Timing	If <5% bone marrow blasts, Consolidation (and/or Option 2): HSCT	
	Chemotherapy containing regimen	Experimental Therapya,b
At least 28 days before HSCT (Day 0)		Interrupt all study therapy.
Confirmed ANC engraftment, 30-60 days post HSCT e		Administer glasdegib 100 mg PO or placebo PO

a. Instructions for glasdegib/placebo dose modifications and Intensive chemotherapy are in Section 5.5.5. Consolidation with cytarabine 3 g/m^2 IV for adults <60 years and 1 g/m^2 for adults ≥60 years over 3 hours twice daily (BID) on Days 1, 3, and 5, every 28 days for up to 4 cycles. Alternative single-agent cytarabine consolidation schedules may be used per local prescribing information.
 
b. Treatment with glasdegib should continue during any delay before the start of another cycle or Induction in the absence of glasdegib-related toxicity that would prevent dosing.
 
c. Where possible, glasdegib will be administered together with daunorubicin IV injection during induction.
 
d. Glasdegib or placebo is administered up to 2 years after randomization unless there is progression, unmanageable toxicity, withdrawal of consent, or CR MRD-negative disease confirmed at 2 consecutive time points post consolidation.
 
e. Confirmed ANC engraftment is defined by ANC ≥0.5 x 10^9/L for 3 consecutive days with no growth factor support following HSCT using myeloablative or non-myeloablative conditioning regimen. 30-60 days post HSCT, glasdegib or placebo may be resumed with ANC engraftment, no ≥ Grade 2 ongoing GVHD, and no ongoing SAEs that prevent resuming glasdegib or placebo maybe present, in the judgement of the investigator.
		

### Induction for Intensive Chemotherapy Study

Subjects will participate in their first induction therapy for a total of 28 days. However, if a subject requires a second Induction therapy due to residual leukemia or investigator opinion, this second course may start as soon as possible following Induction 1 bone marrow evaluation.

If the induction cycle(s) extends longer than 28 days, dosing with glasdegib or placebo should continue daily in the absence of glasdegib-related toxicity that would prevent dosing.

The second induction may be delayed up to an additional 28 days from Day 28 of the first induction to allow for the subject to recover from any severe reversible hematologic or non-hematologic drug related toxicity. Treatment with glasdegib or placebo should continue during any delay before the start of the second induction in the absence of glasdegib-related toxicity that would prevent dosing. The second induction should not be performed if the subject has clinically significant cardiotoxicity (LVEF <45%) and the subject should be discontinued from treatment.

Bone marrow may be repeated at Investigator discretion as required for clinical staging any time prior to next Induction chemotherapy.

The following rules apply for progression from induction to consolidation ([Table 7](#)):

- a. Subjects who successfully obtain a <5% bone marrow blasts after induction are eligible to enter the consolidation phase of the trial 28-days from the start of the last induction. These subjects may also proceed to a second Induction per investigator judgment;
- b. Subjects with residual leukemia at the end of induction 1 may be treated with a second induction therapy;
- c. If after the second induction, the subject still shows residual or resistant leukemia, they must be discontinued from treatment and followed as described in [Section 5.5.2](#). Subjects with resistant leukemia after the first or second course of induction will be discontinued from treatment and followed as described in [Section 5.5.2](#).

Precise timings for the post first induction bone marrow assessment and remission assessment will depend on investigator judgement. In general:

- The **post first induction bone marrow assessment** will occur approximately 14-15 days after initiation of first induction therapy; however, the precise timing will be according to investigator judgment. The post first induction bone marrow assessment is generally done to assess marrow hypoplasia and determine if/when a second Induction is needed. Following the post first induction bone marrow assessment, subjects may complete Induction 1 therapy, start Induction 2 before finishing Induction 1, or end treatment and go to follow-up.
- The remission bone marrow assessment usually occurs approximately 36-48 days after initiation of induction therapy. However, these timings will depend on investigator judgement. The remission bone marrow assessment is generally done to assess hematologic response following Induction therapy. Hematological response will be assessed using the bone marrow results from the remission bone marrow assessment.

### **Consolidation Therapy with a Chemotherapy-containing regimen**

Subjects achieving <5% bone marrow blasts, after the completion of induction therapy are eligible to begin consolidation. Glasdegib will continue to be given at the dose given during induction (unless dose modification due to toxicity is required) once daily in the morning continuously in 28-day cycles, where possible at the same with chemotherapy infusion start.

Subjects can remain on study for a minimum of one but not more than four courses of consolidation if they do not progress during consolidation treatment. If a subject enters consolidation with a CRi (post induction) assessment but then achieves hematologic recovery in the peripheral blood (defined as ANC >1000/ $\mu$ L and platelets  $\geq$ 100,000/ $\mu$ L), the bone marrow evaluation should be repeated within 14 days of the hematologic recovered blood counts observation. Bone marrow examinations may be performed at any time throughout consolidation as clinically indicated to confirm the subject has not relapsed. At a minimum a bone marrow evaluation is required following the final consolidation cycle before any subsequent therapy.

The start of subsequent consolidation cycles may be delayed from the end of the previous cycle to allow for recovery from reversible hematologic or non-hematologic drug-related toxicities. If the consolidation cycle(s) extends longer than 28 days, dosing with glasdegib or placebo should continue daily in the absence of glasdegib-related toxicity that would prevent dosing.

### **Post Remission HSCT**

Subjects who are eligible for Post Remission HSCT will undergo HSCT per local standard of care. For HSCT, Day 0 is the first day of HSCT; this is the day when stem cells are infused.

For post remission HSCT, glasdegib or placebo will be interrupted at least 28 days before HSCT and resumed 30-60 days post date of stem cell infusion, once there is ANC engraftment, no  $\geq$  Grade 2 ongoing GVHD, and no ongoing SAEs that prevent resuming glasdegib/placebo in the judgement of the investigator. Confirmed ANC engraftment is defined by ANC  $\geq 0.5 \times 10^9/L$  for 3 consecutive days without growth factor support following HSCT using myeloablative or non-myeloablative conditioning regimen.

### **Post Consolidation or Post HSCT treatment**

[figure not shown]
Daily glasdegib (100 mg) PO or placebo PO may continue up to 2 years following randomization unless AML is confirmed MRD negative post Consolidation or post HSCT MRD at 2 consecutive time points per central laboratory analysis. These 2 consecutive time points may be approximately 3 months apart as part of the already scheduled marrow assessments.

### 5.5.1.3. Non-Intensive Chemotherapy

For subjects in the Non-Intensive Chemotherapy study, central supply (provided by Pfizer) or locally obtained commercial supplies of azacitidine will be used. Refer to the local package insert (or SPC) or Investigational Product Manual (or SPC) for detailed formulation, preparation and dispensing information.

The general treatment algorithm for the Non-Intensive study is described in Figure 3.

**Figure 3. Non- Intensive Chemotherapy Treatment Algorithm: Glasdegib or Placebo in combination with Azacitidine**

1. Details for azacitidine administration with glasdegib or placebo are described in [Table 8](#).

2. A bone marrow assessment is required when CR is suspected or after end of Cycle 6; whichever, is earlier. BM aspirate is required, and biopsy is preferred. Following Cycle 6, BM assessments will occur when there is an intention for patient to receive HSCT, progressive disease (PD) suspected.

Table 8. Non-Intensive Chemotherapy: Glasdegib or Placebo in Combination with Azacitidine		
Days	Study Treatmenta	
	Chemotherapy	Experimental Therapy
1-7 (±3 day window for each dose)	Administer azacitidine 75 mg/m  SC or IV	Administer glasdegib 100 mg PO or placebo PO
8-28		Administer glasdegib 100 mg PO or placebo PO
Repeat b	Repeat administration of azacitidine 75 mg/m  SC or IV for 7 days as 28 day cycles a	Administer glasdegib 100 mg PO or placebo PO
Timing	If proceeding to HSCT per local Standard of Care	
At least 28 days before HSCT (Day 0)	Interrupt Glasdegib/placebo.	
30-60 days post HSCT c	Resume administration of Glasdegib 100mg PO or Placebo PO d	

a. See Section 5.5.5 for recommended dose modifications/delays/reductions. Since responses to azacitidine may require 4-6 cycles of administration to emerge, treatment with the study drug combination should be continued for at least 6 cycles, or until unacceptable toxicity, patient refusal or death, whichever occurs first. Treatment will be administered in a 28 day cycle, but cycle duration may be extended to allow for toxicity resolution.
 
b. Treatment with the study drug combination should be continued beyond 6 cycles of treatment until objective disease progression or relapse, unacceptable toxicity, patient refusal or death, whichever occurs first.
 
c. Confirmed ANC engraftment is defined by ANC ≥0.5 x 10^9/L for 3 consecutive days with no growth factor support following HSCT using myeloablative or non-myeloablative conditioning regimen. 30-60 days post HSCT, glasdegib or placebo may be resumed with ANC engraftment, no ≥ Grade 2 ongoing GVHD, and no ongoing SAEs that prevent resuming glasdegib or placebo may be present, in the judgement of the investigator.
 
d. Glasdegib or placebo is administered up to 2 years after randomization unless there is progression, unmanageable toxicity, withdrawal of consent, or CR MRD-negative disease confirmed at 2 consecutive time points post consolidation.
		

Subjects will receive either glasdegib 100 mg PO once daily or matching placebo starting on Day 1 and continuing beyond 6 cycles of treatment until objective disease progression or relapse, unacceptable toxicity, patient refusal or death, whichever occurs first.

Azacitidine will be administered per local label or per the Investigational Product Manual (or SPC). The dose for azacitidine is 75 mg/m^2 daily for 7 days to be administered by SC injection or IV infusion in 28 day cycles. Alternate dosing schedule to administer the 7 doses to accommodate subject and treatment center availability is allowed. Dose adjustments will be made according to local approved label or per the Investigational Product Manual (or SPC) for azacitidine.

Since responses to azacitidine may require 4-6 cycles of administration to emerge, treatment with the study drug combination will be continued for **at least 6 cycles**, or until unacceptable toxicity, patient refusal or death, whichever occurs first. In addition, each subsequent cycle may be delayed for up to 28 days to allow for recovery of blood counts. Subjects should continue to receive treatment beyond the Cycle 6, as long as they do not have uncontrollable toxicity, withdrawal consent, and do not meet the criteria for progression.

## **HSCT following CR**

Subjects who are eligible HSCT will undergo HSCT per local standard of care. For HSCT, Day 0 is the first day of HSCT; this is the day when stem cells are infused.

For post remission HSCT, glasdegib or placebo will be interrupted at least 28 days before HSCT and resumed 30-60 days post date of stem cell infusion, once there is ANC engraftment, no  $\geq$  Grade 2 ongoing GVHD, and no ongoing SAEs that prevent resuming glasdegib/placebo in the judgement of the investigator. Confirmed ANC engraftment is defined by ANC  $\geq 0.5 \times 10^9/L$  for 3 consecutive days without growth factor support following HSCT using myeloablative or non-myeloablative conditioning regimen.

Transplant-related information; such as, donor source, type of transplant, and conditioning regimen, must be entered into the CRF.

The HSCT Post Remission Period (HSCT period) is defined as time from the start of the conditioning regimen until the subject restarts glasdegib or placebo, death, post study follow-up, or withdrawal. During the HSCT Consolidation Period, AE collection during the HSCT period is defined in [Section 8](#).

### **Post Consolidation or Post HSCT treatment**

Daily glasdegib (100 mg) PO or placebo PO may continue up to 2 years following randomization unless AML is confirmed MRD negative post HSCT at 2 consecutive time points per central laboratory analysis. These 2 consecutive time points will be approximately 3 months apart as part of the already scheduled marrow assessments.

#### **5.5.2. End-of-Treatment Follow-up**

After discontinuation of study treatment (all arms), post-treatment survival status, response assessments (for those in remission), and hematologic relapse/disease progression will be collected as described in [Table 1](#) and [Table 2](#) for subjects receiving Intensive Chemotherapy and in [Table 3](#) and [Table 4](#) for subjects receiving Non-Intensive Chemotherapy until death or until termination of the study by the Sponsor.

Post treatment follow up visits will occur for the first 2 years. Subjects will return to the site for visits every 3 months starting from the last dose of study medication, for the first 2 years only.

A post treatment long-term follow-up will be completed  $\geq 3$  years starting from the last post treatment follow up visit. A telephone log will include the date of contact and survival data (including date and cause of death) and where possible, subsequent anticancer therapies, including HSCT.

The study will be considered complete once all subjects have been followed for survival for up to 5 years from the first dose of the last subject enrolled in the study, or until death, or consent withdrawal.

### **5.5.3. Food Requirements**

Glasdegib will be administered with a glass of water, with or without food.

### **5.5.4. Treatment Discontinuation**

If a subject demonstrates unequivocal clinically significant disease progression or unacceptable toxicity, they must be discontinued from treatment and followed as described in [Section 6.4](#).

If glasdegib/placebo is permanently discontinued for reasons other than treatment failure, hematologic relapse, objective disease progression, subject refusal, or consent withdrawal, single-agent treatment with azacitidine, or combination daunorubicin and cytarabine may be continued if, in the Investigator's judgment, a clinical benefit has been observed and following discussion between the Investigator and Sponsor.

In cases of unacceptable toxicity or pregnancy, the subject must be withdrawn from study drug combination and entered into the follow-up phase of the study.

When study treatment with both drugs of the study combination (glasdegib/placebo and azacitidine, or cytarabine and daunorubicin) is permanently discontinued, subjects will enter into the follow-up phase.

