### **Discontinuation of Study Therapy for the Non-Intensive Study**

If glasdegib or placebo is permanently discontinued for reasons other than objective disease progression, patient refusal, or consent withdrawal, single-agent treatment with azacitidine may be continued if, in the Investigator's judgment, a clinical benefit has been observed.

In cases of unacceptable toxicity or pregnancy, the patient must be withdrawn from study treatment and entered into the follow-up phase of the study.

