#### **5.5.5.2. Dosing Interruptions for Glasdegib/placebo Non-hematological Toxicities**

Subjects experiencing Grade 3 or 4 non-hematological toxicities potentially attributable to glasdegib or placebo should have their glasdegib or placebo treatment interrupted regardless of when it occurs in the cycle until the toxicity resolves or returns to baseline or  $\leq$  Grade 1, as described in [Table 9](#).

If these parameters have not been met following >28 consecutive days of dose interruption, glasdegib or placebo should be permanently discontinued. If glasdegib or placebo treatment is permanently discontinued, patients may continue single-agent treatment with daunorubicin, cytarabine, or azacitidine, if according to the investigator's judgment a clinical benefit has been observed, and following discussion between the investigator and the sponsor.

**Table 9. Glasdegib or Placebo Dose Modifications for Non Hematologic Toxicities (Excluding QTc Prolongation, Muscle Spasms, and Myalgia)**

Toxicity (NCI CTCAE version 4.03)	Glasdegib or Placebo

≥ Grade 3 toxicity (Nausea, vomiting, and/or diarrhea must persist at ≥ Grade 3 (despite maximal appropriate medical therapy) to require dose modification).
	
Hold study drug until toxicity has recovered to baseline or ≤ Grade 1.
 
First episode: Decrease by 1 dose level.
 
Second episode: Decrease by 1 dose level.
 
Third episode: Permanently discontinue.

Potential DILI/Hy's Law (as defined in Section 8.4.2).
	
Interrupt glasdegib/placebo dosing. If an alternative cause is found, restarting of glasdegib/placebo at the same dose may be considered.

Confirmed DILI/Hy's Law (as defined in Section 8.4.2).
	
Glasdegib/placebo should be permanently discontinued.

Appropriate follow-up assessments should be implemented until adequate recovery (toxicity resolves or returns to baseline) occurs.

Depending on when the adverse event resolved, treatment interruption may lead to the patient missing all subsequent planned doses of glasdegib or placebo within the cycle. If the AE leading to treatment interruption recovers within the same cycle, re-commencement of dosing in that cycle is allowed. Glasdegib or placebo doses omitted for toxicity will not be replaced within that cycle (eg, cycles will not be prolonged beyond the 28 days in order to make up for any missed glasdegib or placebo doses during that cycle).

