### **6.2. Treatment Period**

See the [Schedule of Activities](#) for a detailed list of the assessments and procedures to be collected. Study entry is defined as when the subject is randomized into the IRT system. Subjects must be randomized into the IRT system prior to receiving first dose of study drug.

All assessments on Day 1 of each cycle should be collected pre-dose, unless documented otherwise.

CCI

In cases of unacceptable toxicity or pregnancy, the subject must be withdrawn from study drugs, have an end of treatment visit ([Section 6.3](#)), and be entered into the post-treatment follow-up phase ([Section 6.4](#)).

Subjects who permanently discontinue both study drugs (azacitidine or daunorubicin and cytarabine or glasdegib/placebo) for any reason (except death, or withdrawal of subject consent for follow-up) will enter into the follow-up phase of the study.

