### **6.5. Subject Withdrawal**

Subjects may withdraw from the study at any time at their own request, or they may be withdrawn at any time at the discretion of the investigator or sponsor for safety (see also the [Withdrawal from the Study Due to Adverse Events \(see also the Subject Withdrawal Section\)](#) section) or behavioral reasons, or the inability of the subject to comply with the protocol-required schedule of study visits or procedures at a given study site.

Reasons for withdrawal of study treatment may include:

- Objective disease progression in the Intensive and Non-Intensive Chemotherapy Study or Treatment Failure or Hematologic relapse (Lack of Efficacy) in the Intensive Chemotherapy Study according to the 2017 ELN Recommendations ([Appendix 4](#)):
- Global deterioration of health status requiring discontinuation;

- Unacceptable toxicity (of either study treatment);
- Pregnancy;
- Significant protocol violation;
- Lost to follow-up;
- Subject refused further treatment;
- Study terminated by sponsor;
- Death.

Reasons for withdrawal from study follow-up may include:

- Study terminated by Sponsor;
- Lost to follow-up;
- Withdrawal of subject consent for any further contact;
- Death.

If a subject does not return for a scheduled visit, every effort should be made to contact the subject. All attempts to contact the subject and information received during contact attempts must be documented in the subject's medical record. In any circumstance, every effort should be made to document subject outcome, if possible. The Investigator should inquire about the reason for withdrawal, request that the subject return all unused investigational product(s), request that the subject return for a final visit, if applicable, and follow up with the subject regarding any unresolved AEs.

If the subject withdraws from the study, and also withdraws consent for disclosure of future information, no further evaluations should be performed, and no additional data should be collected. The sponsor may retain and continue to use any data collected before such withdrawal of consent.

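### The protocol gives two incompatible rules on whether the chemotherapy backbone must stop or may continue when glasdegib/placebo is permanently stopped for toxicity

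*Protocol*

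**What the plan says.** **Passages that require everything to stop.** Protocol 5.5.4, first paragraph, makes discontinuation of treatment compulsory for unacceptable toxicity. Its third paragraph says that in such cases "the subject must be withdrawn from study drug combination and entered into the follow-up phase of the study". Section 6.2 says "In cases of unacceptable toxicity or pregnancy, the subject must be withdrawn from study drugs", followed by an end-of-treatment visit and follow-up. The Protocol Summary, under discontinuation of study therapy for the non-intensive study, ends by saying that "the patient must be withdrawn from study treatment and entered into the follow-up phase of the study".

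**Passages that let the backbone continue.** The second paragraph of 5.5.4 concerns a permanent stop of glasdegib/placebo for reasons other than treatment failure, relapse, progression, refusal or withdrawn consent. It says that "single-agent treatment with azacitidine, or combination daunorubicin and cytarabine may be continued if" the investigator sees clinical benefit and has discussed it with the sponsor. The Summary opens the same subsection with a shorter form: "single-agent treatment with azacitidine may be continued if" the investigator judges that there is benefit. Section 5.5.5.2 deals with Grade 3 or 4 non-hematological toxicity potentially due to the blinded drug. It says that after permanent discontinuation "patients may continue single-agent treatment with daunorubicin, cytarabine, or azacitidine", again subject to benefit and sponsor discussion.

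**Reasons for withdrawal.** Section 6.5 includes "Unacceptable toxicity (of either study treatment") in a list of reasons for which study treatment may be withdrawn.

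**The concern.** Both studies ask what glasdegib adds to a common chemotherapy backbone. A site that must manage a patient coming off the blinded drug for toxicity finds a compulsory instruction to end all study treatment and a permission to carry on with chemotherapy. In 5.5.4 the two stand in consecutive paragraphs. Two sites could act differently for the same event, each with protocol text in support.

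Two things are at stake. The first is consistent treatment: whether a patient keeps protocol chemotherapy can depend on the page consulted. The second is interpretation of OS, which is compared in all randomized subjects by assigned arm (Protocol 9.2.1 and 9.3.1, SAP 4.1 and 6.1). If toxicity stops were commoner on glasdegib, sites following the compulsory text would end the backbone more often in that arm, and the OS contrast would include that difference.

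**Working it through.** No figure in the plan decides this point, so the check is mainly a comparison of text.

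**1. The test case.** Take a patient whose glasdegib/placebo is permanently stopped for toxicity attributed to it. The protocol's own triggers include a third episode of Grade 3 or higher toxicity or confirmed DILI (Table 9), Grade 4 QTcF prolongation (Table 10), and no recovery after more than 28 consecutive days of interruption (5.5.5.2).

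**2. The passages side by side.**

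| Place in the protocol | Backbone for this patient | Sponsor discussion | Drugs named |
|---|---|---|---|
| 5.5.4, paragraphs 1 and 3 | must stop | – | treatment; the combination |
| 6.2 | must stop | – | study drugs |
| Summary, last sentence | must stop | – | study treatment |
| 5.5.4, paragraph 2 | may continue | required | azacitidine alone, or daunorubicin with cytarabine together |
| 5.5.5.2 | may continue | required | daunorubicin, cytarabine or azacitidine as a single agent |
| Summary, first sentence | may continue | not mentioned | azacitidine alone |
| 6.5 | not settled | – | either study treatment |

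**3. Can the rows be reconciled from the text?** The permissive rule in 5.5.4 has a closed list of exceptions, and toxicity is not on it, so the test case falls under the permission. The mandatory rule has no exception for toxicity of one drug only. Neither rule refers to the other. Unacceptable toxicity has no definition, and nothing says which passage prevails. For a patient whose toxicity is judged unacceptable, the mandatory and permissive rules cannot both be followed if the backbone is continued.

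**4. Differences within the permissive group.** The table shows two: whether the sponsor must be consulted, and whether the intensive backbone may continue as a combination or only as single agents.

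**5. Effect on the endpoints.** For non-intensive EFS (Protocol 9.3.2, SAP 3.2.1), stopping either study treatment before CRh or better and before completing 6 cycles is already a treatment failure. Both rules therefore give such patients the same EFS event. OS has no such equalizing rule.

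**6. Illustration of size, non-intensive study only.** Start from the plan's figure: 220 deaths and HR 0.64. Fixed-design power is Φ(|ln HR| × √d / 2 − 1.960), that is |ln 0.64| = 0.446, √220 / 2 = 7.416, and Φ(3.310 − 1.960) = Φ(1.350) = 0.91. With the planned boundaries it is about 0.906. The stated 90% is reproduced.

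Next, simulate 320 patients with 23-month uniform accrual, control median 10.4 months, analysis at 220 deaths, and an unstratified log-rank test at z = 1.977 (the final one-sided threshold of 0.024). Assumed shares of each arm stop at a uniform time in months 0 to 6. Afterwards the hazard is that of control (backbone kept), or 1.5 or 2 times control (backbone lost). The stop rates and hazards are assumptions; none is in the documents.

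| Stops, glasdegib vs placebo | Power, backbone kept | Backbone lost, 1.5× | Backbone lost, 2× |
|---|---|---|---|
| none | 0.91 | – | – |
| 7.5% vs 5% | 0.87 | 0.85 | 0.84 |
| 10% vs 5% | 0.85 | 0.825 | 0.80 |
| 15% vs 5% | 0.81 | 0.75 | 0.69 |
| 20% vs 5% | 0.79 | 0.66 | 0.57 |

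Repeat runs agree to within about 0.02. Only the difference from the second column belongs to this point. At 15% vs 5% that is 0.81 − 0.75 = 0.06 to 0.81 − 0.69 = 0.12; at 10% vs 5% it is 0.85 − 0.825 = 0.025 to 0.85 − 0.80 = 0.05. The fall from 0.91 to 0.81 occurs with the backbone kept. The lost-backbone columns also assume that every site follows the mandatory text. With no drug effect and 15% vs 5% stops, one-sided rejection with the backbone lost stayed below 0.024, so false positives are not inflated.

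**The case against.** The strongest defence is that the passages can be read together. Section 5.5.5.2 is the specific rule for toxicity of the blinded drug and could be taken to override the general text. The closing paragraphs of 5.5.4 and 6.2 send patients to follow-up when both drugs have been stopped, which presupposes that one can stop alone. SAP 6.5.2.1 summarizes discontinuation for each drug and counts a patient as off treatment only once all drugs have stopped. SAP 6.6.1 tabulates adverse events leading to withdrawal separately for each drug and for chemotherapy. All of this stands, and it makes the joint reading plausible. But the protocol never states it, and it leaves the must/may conflict inside 5.5.4 in place.

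The defence also limits the consequences, and here it largely succeeds:

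- A reader might infer from "Unacceptable toxicity (of either study treatment") in 6.5 that toxicity of one drug obliges both to stop. The list gives reasons that may lead to withdrawal and does not say which drugs then stop.
- A reader might infer that affected patients lose all leukemia treatment. The mandatory passages end study drugs. Follow-up records new anti-cancer therapy, and no bar on standard chemotherapy after withdrawal was found. The hazards of 1.5 and 2 times control therefore have no basis in the documents.
- Sponsor discussion in both 5.5.4 and 5.5.5.2 limits divergence between sites, though only for those that read the permissive text.
- In the intensive study the backbone is at most two inductions and four consolidation cycles, while the blinded drug can run for up to 2 years. Stops after consolidation have no backbone to lose. The illustration says nothing about that study.

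**Conclusion.** The contradiction stands, in current text, and needs no assumption: for the same toxicity event the protocol both requires the combination to end and allows the backbone to continue, with no definition or precedence to decide between them. The permissive passages also disagree on sponsor discussion and on which drugs may continue.

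The consequence for OS is conditional. A reader might infer that the comparison will be confounded or the trial underpowered. The documents do not support that. They give no discontinuation rates by arm, and Protocol 1.3.2 describes the principal SMO-inhibitor toxicities as mostly Grade 1 or 2 and manageable. Unequal backbone exposure is a possibility if toxicity stops are commoner on glasdegib and sites follow the mandatory text. Its size cannot be estimated. The SAP's by-drug summaries of discontinuation and exposure (6.5.2.1, 6.5.3) would show an imbalance descriptively afterwards but would not prevent it.

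A reader might also infer that the EFS definition must change. It need not, because stopping either treatment before response and before 6 cycles already counts as failure.

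**What to change.** Reconcile the Protocol Summary (discontinuation of study therapy, non-intensive study), 5.5.4, 5.5.5.2, 6.2 and 6.5 into one rule on the backbone after glasdegib/placebo is permanently stopped for toxicity, worded identically in each place. The rule should say what counts as unacceptable toxicity, or which section prevails; whether toxicity of one drug ends one or both; whether sponsor discussion is required; and which backbone drugs are covered in each study, alone or in combination. Which rule to adopt is for the sponsor's clinicians.

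The cost is wording in the next amendment and a letter to sites. No new data, procedures or analyses are needed.
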